## 6.2 Randomization

The randomization sequence will be obtained by computer-generated random numbers and provided to each HVTN CRS through a Web-based randomization system. The randomization will be stratified by the initial HVTN 205 vaccine regimens and be done in blocks to ensure balance across groups. At each institution, the pharmacist with primary responsibility for dispensing study products is charged with maintaining security of the treatment assignments.

## 6.3 Blinding

Participants and site staff (except for site pharmacists) will be blinded as to participant treatment group assignments. Study product assignments are accessible to those HVTN CRS pharmacists, DAIDS protocol pharmacists and contract monitors, and SDMC staff who are required to know this information in order to ensure proper trial conduct. Any discussion of study product assignment between pharmacy staff and any other HVTN CRS staff is prohibited. The HVTN SMB members also are unblinded to treatment assignment in order to conduct review of trial safety.

When a participant leaves the trial prior to study completion, the participant will be told he or she must wait until all participants are unblinded to learn his or her treatment assignment.

Emergency unblinding decisions will be made by the site investigator. If time permits, the HVTN 114 PSRT should be consulted before emergency unblinding occurs.

## 6.4 Statistical analyses

This section describes the final study analysis, unblinded as to treatment group assignment. In addition to analysis of each individual group, the primary analyses will be based on combined groups across different prior priming regimens to maximize the statistical power in the evaluation of the effect of boosting regimens. All data from enrolled participants will be analyzed according to the initial randomization assignment regardless of how many vaccinations they received. In the rare instance that a participant receives the wrong treatment at a specific vaccination time, the Statistical Analysis Plan (SAP) will address how to analyze the participant's safety data. Analyses are modified

intent-to-treat in that individuals who are randomized but not enrolled do not contribute data and hence are excluded. Because of blinding and the brief length of time between randomization and enrollment—typically no more than 4 working days—very few such individuals are expected.

Analyses for primary endpoints will be performed using SAS and R. All other descriptive and inferential statistical analyses will be performed using SAS, StatXact, or R statistical software.

No formal multiple comparison adjustments will be employed for multiple safety endpoints, multiple primary immunogenicity endpoints, or secondary endpoints. However, multiplicity adjustments will be made for certain immunogenicity assays, as discussed below, when the assay endpoint is viewed as a collection of hypotheses (eg, testing multiple peptide pools to determine a positive response).

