Response rates for gp140 declined less than 20% between 2 and 24 weeks after the final MVA boost. Ongoing studies on the durability of different specificities of the responses show that Ab to gp41 and to the IDR of gp41 are much more durable than Ab to gp120 with the former undergoing < 3-fold drops in magnitude between 2 weeks and 24 weeks post the last MVA boost. In contrast, Ab to gp120 drops by about 10-fold in the same period of time.

HVTN 094 demonstrated high response rates for ADCC activity in bound gp120 (Figure 4-7) and bound virion (Figure 4-8), but not the infected cell assay ([name], data not shown). HVTN 094 tested the effect of a 3rd MVA boost for a DNA prime that co-expressed VLPs and GM-CSF. The magnitude of ADCC responses was enhanced by the third MVA boost, suggesting the importance of delivering three MVA inoculations. The 3rd MVA boost was undertaken because the 3-dose MMM regimen had consistently elicited higher Ab responses than the DDMM regimen, which includes only two MVA boosts.

**Figure 4-7 ADCC responses in a bound Bal gp120 assay for HVTN 094 at baseline and after 2nd and 3rd MVA boosts. The assay was conducted by [name] at the Duke HVTN lab.**

**Figure 4-8 ADCC responses in a bound virion (Bal) assay for HVTN 094, at baseline and after 1st and 3rd MVA boosts. The assay was conducted by [name] at the Institute for Human Virology. The magnitudes of ADCC responses were not as high as for infected people ([name], personal communication).**

In summary, MVA/HIV62B has shown good ability to elicit Ab and T cell responses that were still detectable in the majority of responders at 6 months when administered alone or following a DNA prime. The Ab responses have higher binding activity for gp41 than gp120 and much higher levels of serum IgG than serum IgA. The Ab has also had good functional characteristics, with high response rates for ADCC in bound Bal gp120 and bound virion assays and moderate neutralizing activity for laboratory-adapted strains of HIV and Tier 1A patient isolates. Ongoing studies in HVTN 094 indicate that three MVA boosts of a DNA prime are more effective than 2 MVA boosts of a DNA prime. They also indicate that a 3rd MVA dose effectively boosts a 2nd MVA dose and thus justify testing additional MVA doses in the multiple dose MVA/HIV62B regimen.

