## 5 Objectives and endpoints

### 5.1 Primary objectives and endpoints

*Primary objective 1:*

To evaluate the safety and tolerability of MVA/HIV62B and AIDSVAX B/E given separately or together as boost injections after prolonged immunologic rest, to participants who received MVA/HIV62B vaccinations in DDMM and MMM regimens in HVTN 205

*Primary endpoint 1:*

Frequency and severity of local and systemic injection site reactogenicity signs and symptoms, for each boost regimen

Laboratory measures of safety: white blood cells (WBC), neutrophils, lymphocytes, hemoglobin, platelets, ALT, AST, alkaline phosphatase, and creatinine

Frequency of AEs categorized by MedDRA System Organ Class, and MedDRA Preferred Term, severity and assessed relationship to study products; detailed description of all AE meeting DAIDS criteria for expedited reporting

Number of participants with early discontinuation of vaccinations and reason for discontinuation

*Primary objective 2:*

To compare HIV-specific antibody responses elicited by MVA/HIV62B and AIDSVAX B/E given separately or together as boost injections after prolonged immunologic rest

*Primary endpoint 2:*

Frequency, magnitudes and isotypes of Env-specific Ab responses for gp120, gp41, V1/V2, and the IDR of gp41 at 2 weeks after each boost

Neutralizing Ab titers and breadth against the Env vaccine strain (ADA) and heterologous tier 1 and tier 2 strains at 2 weeks after each boost

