### 5.2 Secondary objectives and endpoints

*Secondary objective 1:*

To compare HIV-specific T-cell responses to MVA/HIV62B and AIDSVAX B/E given separately or together as boost injections

*Secondary endpoint 1:*

Frequency and magnitudes of HIV-1 specific CD4+ and CD8+ T-cell responses as measured by ICS at two weeks after each boost

*Secondary objective 2:*

To compare durability of HIV-specific Ab and T-cell responses

*Secondary endpoint 2:*

Frequency, magnitudes and isotypes of Env-specific Ab responses to gp120, gp41, V1/V2, and the IDR of gp41 at 6 months after the final boost

Frequency and magnitudes of HIV-1 specific CD4+ and CD8+ T-cell responses as measured by ICS at 6 months after the final boost

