### 6.4.4 Immunogenicity analysis

#### 6.4.4.1 General approach

For the statistical analysis of immunogenicity endpoints, data from enrolled participants will be used according to the initial randomization assignment. Assay results that are unreliable, from specimens collected outside of the visit window, or from HIV-infected participants postinfection are excluded. Since the exact date of HIV infection is unknown, any assay data from blood draws 4 weeks prior to an infected participant's last seronegative sample and thereafter may be excluded. If an HIV-infected participant does not have a seronegative sample postenrollment, then all data from that participant may be excluded from the analysis.

Discrete categorical assay endpoints (eg, response rates) will be analyzed by tabulating the frequency of positive response for each assay by antigen and treatment group at each timepoint for which an assessment is performed. Response rates will be presented with their corresponding 95% confidence interval estimates calculated using the score test method [31].

To compare the response rates of any 2 groups, a significant difference will be declared if the 2-sided p-value from either a (stratified when appropriate) Barnard's or Fisher's exact test is  $\leq 0.05$ . To compare the response rates among more than 2 groups, first an overall test for any difference in response rate among all groups will be conducted, using a Freeman-Halton exact test (or a Chi-square test, depending on whether there are numbers less than 5 in a given cell of the contingency table). When all pair-wise comparisons between the multiple vaccine groups are of interest, a Tukey-like procedure for proportions as described in [32] will be used. Parametric regression models may also be used to adjust for covariates of interest. More details will be provided in the SAP.

For quantitative assay data (eg, IC50 titer from the neutralizing assay), graphical and tabular summaries of the distributions by antigen, treatment group, and timepoint will be made. For all primary and secondary immunogenicity endpoints, box plots and plots of estimated reverse cumulative distribution curves will be used for graphical display of all of the study groups. Typically the results will be shown for each vaccine group and for the combined groups.

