### **7.3.2 Participant departure from vaccination schedule**

Every effort should be made to follow the vaccination schedule per the protocol. If a participant misses a vaccination and the visit window period for the vaccination has passed, that vaccination cannot be given. The participant should be asked to continue study visits.

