### **7.3.3 Discontinuing vaccination for a participant**

Under certain circumstances, an individual participant's vaccinations will be permanently discontinued. Specific events that will result in stopping a participant's vaccination schedule include:

- Co-enrollment in a study with an investigational research agent (rare exceptions allowing for the continuation of vaccinations may be granted with the unanimous consent of the HVTN 114 PSRT).
- Clinically significant condition (ie, a condition that affects the immune system or for which continued vaccinations and/or blood draws may pose additional risk), including but not limited to the following:
  - Pregnancy (regardless of outcome);
  - Any grade 4 local or systemic reactogenicity symptom, lab abnormality, or AE that is subsequently considered to be related to vaccination;
  - Any grade 3 lab abnormality or other clinical AE (exception: fever or vomiting and subjective local and systemic symptoms) that is subsequently considered to be related to vaccination; or
  - Clinically significant type 1 hypersensitivity reaction associated with study vaccination. Consultation with the HVTN 114 PSRT is required prior to subsequent vaccinations following any type 1 hypersensitivity reaction associated with study vaccination; or
- Investigator determination in consultation with Protocol Team leadership (eg, for repeated nonadherence to study staff instructions).

Such participants should be counseled on the importance of continuing with the study and strongly encouraged to participate in follow-up visits and protocol-related procedures per the protocol for the remainder of the trial, unless medically contraindicated.

In addition, vaccinations will be stopped for participants diagnosed with HIV infection. HIV-infected participants will not continue in the trial (Sections 7.3.4 and 9.7.1).

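### One-boost participants stay in the Day 126 and Day 303 results, where their samples do not fit the boost-anchored endpoints, and no supportive two-boost analysis is planned

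*Combined protocol and SAP*

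**What the plan says.** Section 6.4 sets the analysis population: "All data from enrolled participants will be analyzed according to the initial randomization assignment regardless of how many vaccinations they received". Section 6.4.4.1 repeats it for immunogenicity: "data from enrolled participants will be used according to the initial randomization assignment". The exclusions there are: "Assay results that are unreliable, from specimens collected outside of the visit window, or from HIV-infected participants postinfection are excluded". Not having received boost 2 is not among them.

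Follow-up continues without boost 2. Once the window has passed, Section 7.3.2 says "that vaccination cannot be given. The participant should be asked to continue study visits". Under Section 7.3.3, participants whose vaccinations are permanently discontinued are "strongly encouraged to participate in follow-up visits and protocol-related procedures per the protocol for the remainder of the trial". Section 9.13 keeps pregnant participants in the remaining visits without further injections.

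The endpoints are timed from boosts. Section 5.1 asks for neutralizing titers against the vaccine strain and "heterologous tier 1 and tier 2 strains at 2 weeks after each boost", and gives binding antibody the same timing. Section 5.2 includes "Frequency and magnitudes of HIV-1 specific CD4+ and CD8+ T-cell responses as measured by ICS at 6 months after the final boost", with a matching antibody endpoint. Section 10.3 fixes the primary timepoints at visit 4 (Day 14) and visit 7 (Day 126) and describes the latter by reference to the second vaccination visit.

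**The concern.** The second primary timepoint is meant to show what two boosts elicit, and the 6-month endpoint how long that lasts. Section 4.4 gives the reason for the second boost: one dose of the protein may not raise strong V1V2 responses. A participant who received only the first boost, but still gives blood at Day 126, contributes a late one-boost value to a two-boost result.

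Where antibody wanes quickly, that value will tend to be low. Section 4.8.1.2 says of the earlier trial: "In contrast, Ab to gp120 drops by about 10-fold in the same period of time", the period being weeks 2 to 24 after the last MVA boost. Such values lower an arm's mean and widen its spread. If more people stop in one arm than in the other, they also shift the contrast between arms.

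No existing safeguard deals with this. The 10% allowance in Section 6.1 and the 20% threshold in Section 6.4.4.1 both concern missing data, and a one-boost participant who gives a sample is not missing. Section 6.4.3.4 tabulates discontinuations but does not link them to any immunogenicity analysis.

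**Working it through.** **Timing.** Boosts are at Days 0 and 112 (Table 3-1); visits are at Days 126, 196 and 303 (Appendices F and G). Footnote 7 of Appendix F places the second assay timepoint at M6.5, which matches no visit; I use Day 126 from Section 10.3.

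- Two boosts: 126 − 112 = 14 days; 303 − 112 = 191 days.
- One boost: 126 − 0 = 126 days; 303 − 0 = 303 days.
- A one-boost participant's draw nearest to 6 months is visit 8: 196 − 0 = 196 days. Appendix F schedules binding and neutralizing serum there, but no ICS sample.

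**The plan's own figure.** Noncentral t power (two-sided 0.05, effect size 1) gives 83.0% for 18 v 18, 98.7% for 36 v 36 and 92.5% for 18 v 36. Table 6-5 states 83%, 99% and 92%, so it reproduces.

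**Drop from waning (assumption).** Take the 10-fold gp120 fall as log-linear over 22 weeks and applicable after these boosts. Day 126 is 16 weeks later than a 2-week sample: 1.0 × 16/22 = 0.73 log10. I vary this from 0.3 to 1.0. For gp41 and its IDR the reported fall is under 3-fold, so the drop is below 0.477 × 16/22 = 0.35 log10.

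**Effect on an arm's mean.** Shift = −share × 0.73. A 10% share gives −0.073 log10 (geometric mean about 15% lower); 20% gives −0.145 (about 28% lower).

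**Effect on comparisons.** Assumptions: SD 0.5 (Section 6.1.2 gives 0.1 to 1.2), true difference 0.5, one-boost values lowered by the drop, group difference otherwise kept. Two-sample t tests were simulated, 40,000 per scenario. Each cell gives the result for a drop of 0.73, with the range for drops of 0.3 to 1.0 in brackets.

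| One-boost participants | Mean difference | Power |
|---|---|---|
| 18 v 18, none | 0.50 | 83% |
| 18 v 18, 2 and 2 | 0.50 | 77% (82–72%) |
| 36 v 36, none | 0.50 | 98.7% |
| 36 v 36, 4 and 4 | 0.50 | 97.9% (98.6–96.7%) |
| 18 v 18, 1 in lower and 3 in higher arm | 0.42 (0.47–0.39) | 61% (77–48%) |
| 36 v 36, 2 in lower and 6 in higher arm | 0.42 (0.47–0.39) | 91% (97–83%) |

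The shrinkage in the unequal case is direct: 0.50 − 0.73 × (3/18 − 1/18) = 0.42. For 18 v 36 with 2 and 4 one-boost participants, power goes from 92.5% to about 89%. With a gp41-type drop of 0.35, the 2 and 2 case at 18 v 18 stays near 82%.

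**If the group difference is also lost.** The table counts waning only. If one-boost participants show no group difference at all, a 10% share in each arm gives an average variance of 0.25 + 0.09 × (0.727² + 1.227²)/2 = 0.3415. The effect size is then 0.9 × 0.5/√0.3415 = 0.77, with power 61% for 18 v 18 and 90% for 36 v 36.

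**What a two-boost subset would cost.** Dropping 2 per arm leaves 16 v 16 with 78% power; dropping 4 leaves 32 v 32 with 98%.

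**The case against.** Analysing as randomised whatever was received is an open and defensible choice, and it protects the comparison. Section 10.3 ties the timepoints to visits, and Sections 5.1 and 5.2 do not say that the boost must actually have been given. All of this stands. It means that the as-randomised result should remain primary, not that it answers the two-boost question for people who had one boost.

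A reader might infer that the trial's power drops to 77% or 61%. The documents do not support that as a general statement. Those figures belong to single-group comparisons with gp120-type waning, and the 61% in the table also needs unequal stopping. Sections 6.1 and 6.4 base the primary analyses on combined groups, where equal stopping costs less than one percentage point under the waning model. Nor does the subset recover much power: 78% against 77% in the equal case. Its value is in interpretation.

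A reader might also infer that the more reactogenic arm will look less immunogenic. That is possible but not shown. Section 7.3.3 exempts fever, vomiting and subjective symptoms from its grade 3 criterion, and pregnancy, co-enrolment, nonadherence and missed windows also end or prevent vaccination. Section 4.8.1.1 reports few severe reactions in HVTN 205: 2 participants local and 4 systemic.

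Finally, the visit windows are in the Study Specific Procedures, and Section 6.4.4.1 defers some test and model details to the SAP. If windows ran from the actual date of boost 2, these samples might be excluded as out of window; nothing in the documents says so.

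**Conclusion.** The mismatch holds on the text. A one-boost participant who stays in follow-up enters the Day 126 and Day 303 results with samples that do not meet the stated timing, and the documents contain neither a two-boost analysis nor a rule for such participants. Day 14 is unaffected, as are participants who leave and give no later samples.

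The likely effect is modest for the combined comparisons and larger for individual groups and fast-waning specificities. All the power figures rest on an assumed one-boost share, since the plan gives none, and on waning carried over from HVTN 205; they are ranges, not corrections to Table 6-5. The goal in Section 6.1.2 is preliminary estimation, so the lower arm means and the mislabelled durability values matter at least as much as power.

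A reader might conclude that the analysis population is wrong, or that conclusions should rest on two-boost recipients. Neither follows: that subset is formed after randomisation, and if stopping did differ by arm it would itself be open to selection. The point is a cheap improvement in interpretability.

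**What to change.** Keep the as-randomised analysis as primary. In the SAP, before unblinding:

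- For Day 126 and Day 303, prespecify a supportive analysis limited to participants who received both boosts in window. Give the number excluded and the reasons by group, and report it beside the primary result with the caveat that randomisation does not protect it.
- Do not label one-boost participants' Day 303 values as 6 months after the final boost. Where antibody assays are run at visit 8 (Day 196), list those values separately as their 6-month antibody result.
- State whether a Day 126 or Day 303 sample from a participant without boost 2 counts as in window.

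Cost: one extra set of tables and possible selection in the subset. Section 10.3 and footnote 7 of Appendix F make assays at other timepoints contingent, so a few additional assays on serum already scheduled may be needed. The T-cell endpoint has no visit 8 substitute because no ICS sample is drawn there.

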#### **6.4.1 Analysis variables**

The analysis variables consist of baseline participant characteristics, safety, and immunogenicity for primary- and secondary-objective analyses.

#### **6.4.2 Baseline comparability**

Treatment groups will be compared for baseline participant characteristics using descriptive statistics.

#### **6.4.3 Safety/tolerability analysis**

Since enrollment is concurrent with receiving the first vaccination, all participants will have received at least 1 vaccination and therefore will provide some safety data.

##### **6.4.3.1 Reactogenicity**

The number and percentage of participants experiencing each type of reactogenicity sign or symptom will be tabulated by severity and treatment group and the percentages displayed graphically by group. For a given sign or symptom, each participant's reactogenicity will be counted once under the maximum severity for all injection visits. In addition to the individual types of events, the maximum severity of local pain or tenderness, induration or erythema, and of systemic symptoms will be calculated. Kruskal-Wallis tests will be used to test for differences in severity between groups.

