### 9.3 Enrollment and vaccination visits

Enrollment is simultaneous with first vaccination. The time interval between randomization and enrollment should not exceed 4 working days. The HVTN CRS registers the participant by scheduling the day 0 visit (enrollment) via the Web-based randomization system, and requests the randomization assignment. Circumstances may require a participant's enrollment visit to be changed. This may exceed the 4-day randomization time limit.

At all vaccination visits, the following procedures are performed before vaccination:

- Abbreviated physical examination, including weight, vital signs, and a symptom-directed evaluation by history and/or appropriate physical exam based on participant self-reported symptoms or complaints;
- Assessment of baseline reactogenicity parameters;
- Assessment of concomitant medications (as described in Section 9.2);
- Cardiac symptom assessment;
- Assessment of any new or unresolved AEs/intercurrent illnesses; and
- Urine or serum pregnancy test (for participants who were born female). Persons who are NOT of reproductive potential due to having undergone total hysterectomy or bilateral oophorectomy (verified by medical records), are not required to undergo pregnancy testing.
- Optional mucosal specimen collection
- Clinical laboratory tests for study participants who agree to provide (semen, rectal, or cervicovaginal) mucosal secretion samples, including:
  - Syphilis
  - Gonorrhea and chlamydia
  - Trichomonas vaginalis (for participants providing cervicovaginal samples),
  - Bacterial vaginosis (for participants providing cervicovaginal samples),
  - Yeast (for participants providing cervicovaginal samples, if clinically indicated).

Following completion of all procedures in the preceding list, and if results indicate that vaccination may proceed, vaccination is prepared and administered (Sections 8.3 and 8.4).

Administration of all injections during a vaccination visit must be accomplished within 1 calendar day.

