## 9.10 Assessments of reactogenicity

For all participants, baseline assessments are performed before and reactogenicity assessments are performed after each vaccination. All reactogenicity symptoms are graded according to the Division of AIDS Table for Grading the Severity of Adult and Pediatric Adverse Events (DAIDS AE Grading Table), Version 2.0 [November 2014], except as noted in Section 11.2.2).

The reactogenicity assessment period is 3 full days following each vaccination per the assessment schedule shown in Table 9-1. Participants are instructed to record symptoms using a postvaccination symptom log and to contact the site daily during the assessment period. Clinic staff will follow new or unresolved reactogenicity symptoms present at day 3 to resolution. Participants are instructed to contact the clinic for events that arise during the period between vaccination and the next scheduled visit. In general, a participant who self-reports any postvaccination reaction greater than mild is seen by a clinician within 48 hours after onset, unless the reaction is improving and/or has completely resolved.

Reactogenicity events are reported using CRFs that correspond to the time of assessment in Table 9-1. Reactogenicity assessments include assessments of systemic and local symptoms, vaccine-related lesions, and lymph nodes. Events not listed on a CRF, or with an onset after the reactogenicity assessment period (day of vaccination and 3 full days after), or those meeting SAE/adverse events requiring expedited reporting to DAIDS criteria, are recorded on an adverse experience log form.

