**Table 9-1 Schedule of reactogenicity assessments**

| Day            | Time                                       | Performed by                  |
|----------------|--|-------------------------------|
| 0 a | Baseline: before vaccination               | HVTN CRS staff                |
|                | Early: 25-60 minutes after vaccination     | HVTN CRS staff                |
|                | Between early assessment and 11:59pm day 0 | HVTN CRS staff or participant |
| 1              | Between 12:00am and 11:59pm day 1          | HVTN CRS staff or participant |
| 2              | Between 12:00am and 11:59pm day 2          | HVTN CRS staff or participant |
| 3 b | Between 12:00am and 11:59pm day 3          | HVTN CRS staff or participant |

a Day of vaccination

b New or unresolved reactogenicity symptoms present on day 3 are followed until resolution

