### 9.10.1 Assessment of systemic and local symptoms

Systemic symptoms include increased body temperature, malaise and/or fatigue, myalgia, headache, chills, arthralgia, nausea, and vomiting. Local symptoms include pain and/or tenderness proximal to the injection site. The daily maximum severity reached for each symptom during the assessment period is reported.

Body temperature is measured by oral or infrared thermometry and reported in degrees Celsius. If temperature is measured in Fahrenheit, the conversion to Celsius should be documented in the participant's chart note. A measurement is taken once daily during the assessment period and should be repeated if participant is feeling feverish.

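### Section 6.4.3.1 scores reactogenicity at the raw maximum and plans no use of the pre-injection assessment, so unworsened pre-existing systemic symptoms inflate the absolute rates in primary endpoint 1.

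*Combined protocol and SAP*

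**What the plan says.** The first component of primary endpoint 1 in Section 5.1 is: "Frequency and severity of local and systemic injection site reactogenicity signs and symptoms, for each boost regimen". Section 6.4.3.1 gives the only scoring rule: "For a given sign or symptom, each participant's reactogenicity will be counted once under the maximum severity for all injection visits". The same section takes maxima over local pain or tenderness, over induration or erythema, and over systemic symptoms. It then adds: "Kruskal-Wallis tests will be used to test for differences in severity between groups". None of this refers to the participant's state before the injection.

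That state is recorded. Section 9.3 lists, among the procedures done before each vaccination, "Assessment of baseline reactogenicity parameters". Table 9-1 has a day 0 row, "Baseline: before vaccination". Section 9.10 says "baseline assessments are performed before and reactogenicity assessments are performed after each vaccination".

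The systemic list in Section 9.10.1 is unspecific: "Systemic symptoms include increased body temperature, malaise and/or fatigue, myalgia, headache, chills, arthralgia, nausea, and vomiting".

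For laboratory values, by contrast, Section 6.4.3.3 does plan changes from baseline. Table 3-1 shows an active product in every group. Groups 1, 3 and 5 have saline in one deltoid only.

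**The concern.** The endpoint is meant to describe reactions to each boost regimen. Under the rule as written, a participant with a mild headache before the injection and the same headache that evening is tabulated with Grade 1 systemic reactogenicity. A participant with moderate fatigue before the Day 112 injection and mild fatigue that day and the next is tabulated at the mild grade, although the symptom improved. Taking a maximum over eight non-specific symptoms and two visits gives such cases several chances to enter.

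The main product of a small phase 1 safety analysis is the absolute rate per regimen. With no saline-only arm, a reader cannot judge how much of a systemic rate was there beforehand. The pre-injection record speaks directly to that question, and the plan makes no use of it.

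**Working it through.** **Is there a plan figure to reproduce?** There is none for pre-injection symptoms. For scale, Section 6.1.1 gives an upper 95% score bound of 16.1% for 0/20. This reproduces: z²/(n + z²) = 3.84/(20 + 3.84) = 16.1%.

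**Does the baseline record itself enter the maximum?** The text leans towards no but does not settle it.
- Section 9.10 words baseline assessments as separate from reactogenicity assessments and sets the period as 3 full days following vaccination.
- The same section later describes the period as including the day of vaccination, and ties the case report forms to the times in Table 9-1. That table is titled as the schedule of reactogenicity assessments and includes the baseline row.

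Whichever reading is taken, a post-injection record of an unchanged symptom is scored at its grade.

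**Size.** Inputs, all assumed because the documents give none:
- p: share with any systemic symptom before a given injection, 5 to 15%.
- s: share of those still symptomatic afterwards, 0.5 to 0.75.
- r: true rate of any systemic reaction over the two visits, 25% or 50%.
- Visits are independent of each other, and pre-existing symptoms are independent of true reactions.

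The probability of a carried-over symptom at one or both visits is q = 1 − (1 − ps)². Only participants with no true reaction are added to the count, so the excess is (1 − r) × q.

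| p | s | ps | q | excess, r = 25% | excess, r = 50% |
|---|---|---|---|---|---|
| 5% | 0.5 | 0.025 | 4.9 | 3.7 | 2.5 |
| 5% | 0.75 | 0.0375 | 7.4 | 5.5 | 3.7 |
| 10% | 0.75 | 0.075 | 14.4 | 10.8 | 7.2 |
| 15% | 0.75 | 0.1125 | 21.2 | 15.9 | 10.6 |

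The last three columns are in percentage points. In a group of 20 the two ends are 0.7 to 3.2 participants at r = 25% and 0.5 to 2.1 at r = 50%.

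**Dilution.** The tabulated rate is r + (1 − r)q, so a true difference between two groups shrinks by the factor (1 − q). An assumed contrast of 25% against 55% (30 points) becomes 30 × 0.951 = 28.5 points at the low end and 30 × 0.788 = 23.6 points at the high end. Take n = 40 per group (Groups 1 and 3 against Groups 2 and 4), two-sided 0.05 and a normal approximation for two proportions. Power is then 79% with no carry-over, 75% at ps = 2%, 69% at 5% and 59% at 10%. This illustrates the direction and rough scale. It is not the power of the planned Kruskal-Wallis test.

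**The case against.** The strongest reply is that the plan is silent rather than wrong, and that the trial's conduct already limits the problem.

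- **Silence.** A reader might infer that the plan directs baseline symptoms to be counted, or discards the baseline data. The documents say neither. Section 9.10 keeps baseline and post-injection assessments apart in its wording. What stands is that no rule sets a post-injection symptom against its pre-injection grade.
- **Safeguards.** Section 7.3.1 lists pre-vaccination symptoms that may mask a vaccine reaction among the factors for delaying an injection. Section 9.3 makes vaccination conditional on the preceding checks. Exclusion 23 in Section 7.2 removes confusable conditions at entry. These lower p. They do not bring it to zero: delay is one factor to consider, the exclusion applies at enrollment, and none of them says how to score a participant who is injected with a symptom present.
- **Bias between regimens.** A reader might infer that one boost is made to look worse than another. Section 6.2 stratifies randomization by prior regimen, so pre-existing symptoms balance in expectation within the DDMM and MMM strata. Only comparisons across prior regimens lack that protection.
- **Magnitude.** Multiplying q by 20 gives about 1 to 4 participants, but that assumes nobody has a true systemic reaction. The factor (1 − r) is needed.
- **Local reactions.** Pain or induration at a site not yet injected is unlikely. The saline deltoid in Groups 1, 3 and 5 could serve as a within-person reference, although no by-deltoid analysis is planned.
- **The remedy has limits.** One pre-injection snapshot cannot remove background symptoms that first arise on days 0 to 3, so it does not replace a saline arm. Counting only worsened grades also loses a symptom that the vaccine prolongs at the same grade. A raw maximum avoids undercounting, which is a defensible choice in phase 1. This is a sound reason to keep the raw table, but not a reason to present it alone.

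**Conclusion.** The point holds for systemic symptoms. Section 6.4.3.1 gives a raw maximum and no companion analysis that uses the pre-injection assessment, so absolute systemic rates per regimen are inflated by an unknown amount and contrasts are somewhat diluted. Under the assumed p, s and independence, the excess runs from about 3.7 to 15.9 points at r = 25% and from 2.5 to 10.6 points at r = 50%. If symptoms are rarer before injection than 5%, it is smaller. The documents do not support a claim of directional bias between boost regimens within a stratum, of a material effect on local reactions, or that the raw maximum should be dropped. Because the stated endpoint is the rate for each regimen, which randomization does not correct, the addition is worth making.

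**What to change.** In Section 6.4.3.1:

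1. State that the pre-injection record does not enter the maximum.
2. Keep the table of raw post-injection maximum severity.
3. Add beside it a table, with the same Kruskal-Wallis test, of signs and symptoms whose post-injection grade through day 3 exceeds the grade recorded before that visit's injection, taking the maximum over visits of those worsened grades.
4. Report pre-injection symptom prevalence by group and visit.

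The cost is one derivation and the extra tables. The data are already collected, and no visit, procedure or sample size changes. The added table misses symptoms that the vaccine prolongs at an unchanged grade. The retained raw table covers those.
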